9.5 EXPLORATORY ANALYSIS

Data collected from the exploratory arm will be used to examine exploratory hypotheses. In addition to the data collected from clinical measurements and questionnaires, this arm will also provide data via the App. The App will collect information regarding usage of features, food choice on the App, amongst other App utilisation parameters. This data will be used to explore:

- the efficacy of implementing a DNA-based diet using an App to improve glucose regulation in pre-diabetic patients
- the utility of the App to participants in both practical terms (e.g. saving time on food choices), and aspiration terms (encouragement to pursue a more healthy lifestyle).
- the aspects of the App that were the most/least effective
- how the App influences adherence levels of participants to a healthier lifestyle

Additional exploratory analyses may be performed using this arm, if the data suggest other effects of interest.

10 REGULATORY ISSUES

10.1 ETHICS APPROVAL

The Chief Investigator has obtained approval from the North of Scotland REC 1. The study must be submitted for HRA and CCC approval at each participating NHS Trust. The Chief Investigator will require a copy of the Trust R&D approval letter before accepting participants into the study. The study will be conducted in accordance with the recommendations for physicians involved in research on human subjects adopted by the 18th World Medical Assembly, Helsinki 1964 and later revisions.

10.2 CONSENT

Consent to enter the study must be sought from each participant only after a full explanation has been given, an information leaflet offered and time allowed for consideration. Signed participant consent should be obtained. The right of the participant to refuse to participate without giving reasons must be respected. After the participant has entered the study the clinician remains free to give alternative treatment to that specified in the protocol at any stage if he/she feels it is in the participant's best interest, but the reasons for doing so should be recorded. In these cases the participants remain within the study for the purposes of follow-up and data analysis. All participants are free to withdraw at any time from the protocol treatment without giving reasons and without prejudicing further treatment.

Please see Appendix 5 for an example consent form.

10.3 CONFIDENTIALITY

The Chief Investigator will preserve the confidentiality of participants taking part in the study. Following the consent of participants, a participant's GP may be informed of significant findings from physical examination or laboratory tests.

It will be necessary for DnaNudge Ltd to be transferred the following **anonymised** data:

- Genetic results
- Participant ID
- Year of Birth
- Ethnicity
- Sex

This is necessary in order for the algorithms of DnaNudge Ltd to compute the DNA-based dietary guidelines that will be provided to participants in the intervention and exploratory arms. For participants in the exploratory arm, it will also be required to provide participants with an App to provide the DNA-based dietary guidelines and to guide their grocery shopping choices. Of note, DnaNudge Ltd will not receive the names of participants, the only data that will be transferred will be anonymised.

The following is a statement from DnaNudge Ltd. regarding the security of the data which they will hold for the ASPIRE-DNA trial:

“How personal information is protected? For the data governance approval Buccal mucosal cells samples from the inner side of the cheek and the oral cavity of the participant will be processed in a small genetic testing device (NudgeBox). The end-to-end processing of the sample includes inserting the swab sample into the disposable cartridge, placing the cartridge in the NudgeBox and extracting DNA from the swab sample (a process that can be controlled by the participant’s mobile device), amplifying DNA, and analysing genetic results. The sample-containing cartridge is single use only and is disposed upon completion of the test. An additional 2ml saliva sample of the participant will be anonymised and processed with conventional DNA analysis methods (e.g. PCR, and RT-PCR analysis) at the Imperial College laboratory facilities. Both genetic analyses, carried out either by the NudgeBox or at the Imperial College laboratories, will not examine the whole genetic sequence of the participant, but will be focuses on isolated partial genetic information (i.e. single-nucleotide polymorphism SNPs) that will give us an insight in how a participant is metabolises food, how different nutrients affect his/her body, and what impact different ingredients have on the participant in the long term. To the best of our knowledge, the genetic results provided by our test will not be informative enough to trace the personal details of an individual; furthermore, we will not perform any test to trace personal details. The genetic results, which are encrypted and protected by the password set by the participant, will be stored in the participant’s mobile device App. The genetic results are also anonymised, encrypted, and backed-up in a password-protected and secure cloud service (i.e. AWS) maintained by DnaNudge when the mobile device is connected to the internet. The genetic results are separated from other data in cloud storage and are secured by password-protected mechanism in which only the user can access his/her own results through the App using his/her log-in and participant ID.

Data deletion

If a participant would like to have all his/her data deleted, his/her account will be deleted in the cloud and he/she will not be able to access his/her App. All his/her data (such as genetic results and shopping records) and the back-up will be deleted in the cloud.”

10.4 INDEMNITY

Imperial College London holds negligent harm and non-negligent harm insurance policies which apply to this study. Imperial College Healthcare NHS

Trust holds standard NHS Hospital Indemnity and insurance cover with NHS Litigation Authority for NHS Trusts in England, which apply to this study.

10.5 SPONSOR

Imperial College London will act as the Sponsor for this study. Delegated responsibilities will be assigned to the NHS trusts taking part in this study.

10.6 FUNDING

This study will be funded via a clinical trial agreement between Imperial College London and DnaNudge Ltd. Participants will be reimbursed for any travel expenses incurred, or greater than normal grocery expenses during the course of the trial.

10.7 AUDITS

The study may be subject to inspection and audit by Imperial College London under their remit as sponsor and other regulatory bodies to ensure adherence to GCP and the UK Policy Framework for Health and Social Care Research.

11 DATA HANDLING AND RECORD KEEPING

11.1 DATA COLLECTION AND MANAGEMENT RESPONSIBILITIES

Data collection is the responsibility of the clinical trial staff at the site under the supervision of the site PI. The Investigator is responsible for ensuring the accuracy, completeness, legibility, and timeliness of the data reported.

All source documents should be completed in a neat, legible manner to ensure accurate interpretation of data. When making changes or corrections, cross out the original entry with a single line, and initial and date the change.

Copies of the electronic CRF (eCRF) will be provided for use as source documents and maintained for recording data for each participant enrolled in the study. Data reported in the eCRF derived from source documents should be consistent with the source documents or the discrepancies should be explained and captured in a progress note and maintained in the participant's official electronic study record.

Clinical data (including AEs, concomitant medications, and expected adverse reactions data) and clinical laboratory data will be entered into password-protected hard-drives. The data system includes password protection and internal quality checks to identify data that appear inconsistent, incomplete, or inaccurate. Clinical data will be entered directly from the source documents. Data collected in the study will be stored in the Imperial Clinical Research Facility for the duration of the trial. A back up of the data will be transferred to the Centre for BioInspired Technology at Imperial College London on a weekly basis during the trial via a password-protected hard-drive. The hard-drive will be transported by designated individuals using the Imperial Shuttle Bus. After trial completion, the remainder of the data will be transferred to the Centre for Bio-Inspired Technology at Imperial College London. This includes the Site Files and Participant Notes. Both during and after the trial, anonymised genetic information, sex, ethnicity and year of birth will be transferred to the DnaNudge cloud to compute the DNA-based dietary guidelines.

Trial data, blood samples and saliva samples may be used in future research by research studies in Imperial College London and in other organisations. These organisations may be universities, NHS organisations or companies involved in health and care research in this country or abroad. The information will only be used by organisations and researchers to conduct research in accordance with the UK Policy Framework for Health and Social Care Research.

11.2 STUDY RECORDS RETENTION

Study documents should be retained for a minimum of 10 years after the completion of the trial. These documents should be retained for a longer period, however, if required by local regulations.

11.3 PROTOCOL DEVIATIONS

A protocol deviation is any noncompliance with the clinical trial protocol, or GCP requirements. The noncompliance may be either on the part of the participant, the Investigator, or the study site staff. As a result of deviations, corrective actions are to be developed by the site and implemented promptly.

These practices are consistent with ICH E6:

- 4.5 Compliance with Protocol, sections 4.5.1, 4.5.2, and 4.5.3
- 5.1 Quality Assurance and Quality Control, section 5.1.1
- 5.20 Noncompliance, sections 5.20.1, and 5.20.2.

It is the responsibility of the site to use continuous vigilance to identify and report deviations within 7 working days of identification of the protocol deviation, or within 7 working days of the scheduled protocol-required activity. All deviations must be addressed in study source documents, reported to the Trial Manager and the study Sponsor. Protocol deviations must be sent to the local IRB as per their guidelines. The site study staff is responsible for knowing and adhering to their IRB requirements.

12 STUDY MANAGEMENT

The Steering Committee will govern the conduct of the study. The Steering Committee will be composed of the CI [name], Co-Investigators [name] and [name], and Trial Manager, [name]. The Steering Committee will meet in person at least quarterly. The day-to-day management of the study will be co-ordinated by [name].

12.1 TRIAL MONITORING

The monitoring plan has been devised and will be approved by the Sponsor before the trial begins.

12.2 TRIAL Suspension

In the event of the Imperial College Healthcare NHS Trust issuing a suspension of all non-essential clinical research activity, such as during the outbreak of COVID-19 in early 2020, all clinical visits to the ICRF will be suspended for the duration of the suspension. Phone-call visits will continue to be performed, as advised from the ICRF. For any participants for whom their clinical visits were to fall within the suspension period, their intervention period will be extended by the length of the suspension and their visits will re-commence once clinical research has resumed.

## Abbreviations

BMI	Body Mass Index
CRF	Case report form
DBP	Diastolic Blood pressure
DNA	Deoxyribonucleic acid
FFQ	Food Frequency Questionnaire
FPG	Fasting Plasma Glucose
HDL	High-density lipoprotein
HOMA	Homeostasis model assessment of beta cell function
IFT	Impaired fasting glucose
IGR	Impaired Glucose regulation
IGT	Impaired glucose tolerance
IQR	Inter quartile range
IRI	Insulin resistance index
ITT	Intention to treat
LDL	Low-density lipoprotein
LMM	Linear mixed model
LTFU	Loss to follow up
OGTT	Oral glucose tolerance test
PG120	Plasma glucose at 12 minutes
QQ plot	Quantile – quantile plot
REML	Restricted Maximum Likelihood
SNP	single nucleotide polymorphisms
SBP	Systolic blood pressure

## Background

Diabetes is amongst the most common long term conditions, with the number of people affected worldwide quadrupling from 108 million in 1980 to 422 million in 2014. Its prevalence in people over 18 years of age has risen from 4.7% in 1980 to a staggering 8.5% in 2014. In 2012, there were 1.5 million deaths as a direct result of diabetes, making it the 8th leading cause of death amongst both sexes, and the 5th leading cause of death amongst women. There were a further 2.2 million deaths as a result of complications due to higher-than-optimal glucose levels. In 2013, 6% of the UK adult population (2.7 million people) were diabetic, 90% of whom had type 2 diabetes. A further 5 million people were estimated to be at high risk of developing type 2 diabetes (NHS n.d.). This has led to a cost of £8 billion per year to the NHS, 80% of which is due to diabetes-related complications such as cardiovascular disease, amputations, renal failure and sight loss.

The potential for lifestyle interventions to prevent type 2 diabetes in high-risk patients has been well demonstrated through various clinical trials. Yet there is important variation in the response between individuals who receive lifestyle interventions because of behavioural factors such as personal motivation and adherence but also because of genetic factors. When personalised, the lifestyle interventions could achieve greater effectiveness by optimising and adapting the intervention components to individuals' goals and characteristics as well as enhancing motivation to adhere to dietary advice. There is a need to determine the most-cost effective personalised interventions and how they could be applied.

The ASPIRE study aims to assess the use of genetic data to guide personalised nutrition in people with impaired glucose tolerance and to demonstrate the impact of personalised nutrition on glucose metabolism, anthropometry, non-glucose metabolism and lifestyle.

In this trial, it is assumed that DNA-based dietary advice is more effective in improving glucose metabolism in pre-diabetic participants compared to the advice received as part of standard care for pre-diabetic individuals. A DNA-based diet is also assumed to improve anthropometric measurements, lipid profile and blood pressure in pre-diabetic participants. If participants from the intervention arm are found to have lower fasting plasma glucose (FPG) compared to patients from the control arm, this will provide evidence that DNA-based dietary advice is an effective way to prevent diabetes.

This document details the planned analyses and endpoints derivation for the ASPIRE-DNA study.

## **Study objectives**

### **1.1 Primary objectives**

- To compare differences in the impact of a DNA-based diet and standard care in improving glucose regulation in pre-diabetic individuals

### **1.2 Secondary objectives**

- To assess the ability of a DNA-based diet to improve the macro- and micro-nutrient profile of pre-diabetic participants.
- To assess the effect of a DNA-based diet on clinical markers including cholesterol, body composition and blood pressure, as they relate to diabetes risk.
- Where applicable, to assess changes in anthropometric measurements as a result of following a DNA-based diet, where they relate to diabetic risk reduction.

### **1.3 Exploratory objectives**

- To assess the impact of providing DNA-based dietary guidelines via the DnaNudge App, on improving glucose regulation in pre-diabetic individuals
- To assess the impact of providing DNA-based dietary guidelines via the DnaNudge App, on the secondary outcomes outlined above.
- To explore the utility of an app as a delivery mechanism for DNA-based dietary advice.
- To examine the changes in leptin measurements via saliva samples during the study.

## Study design

Open label randomised control trial. Participants will be randomised 1:1:1 to a) the control arm (n = 60) in which they will receive general health guidelines according to the NICE guidelines, b) the intervention arm (n = 60) in which they will receive DNA-based health guidelines via a genetic report, or to c) the exploratory arm (n = 60) in which they will receive DNA-based guidelines via the DnaNudge App.

The primary analysis will focus on the comparison between intervention arm and control arm.

## Definitions

Impaired glucose regulation: impaired fasting glucose (IFG) or impaired glucose tolerance (IGT).

Impaired fasting glucose:

$6.1\text{ mmol/L} \leq \text{Fasting plasma glucose (FPG)} \leq 6.9\text{ mmol/L}$  AND  $2\text{ hr plasma glucose: } < 7.8\text{ mmol/L}$

Impaired glucose tolerance:

- $\text{FPG} \geq 7\text{ mmol/L}$  AND  $7.8\text{ mmol/L} \leq \text{2-hour plasma glucose} < 11\text{ mmol/L}$  after glucose load
- HbA1c between 42 and 47 mmol/mol (6.0–6.4%)

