3.3 STUDY POPULATION

Adults with impaired glucose regulation defined by HbA1c, impaired fasting glucose (IFG) or impaired glucose tolerance (IGT) in line with WHO criteria (N = 180):

HbA1c:

- < 42 mmol/mol (6.0%): Non-diabetic
- 42 < 47 mmol/mol (6.0–6.4%): IGT – Pre-diabetic
- ³ 48 mmol/mol (6.5%): Type 2 diabetic

| IFG (World Health Organization 2006):

- Fasting plasma glucose: 6.1mmol/L (110mg/dL) ≤ IFG ≤ 6.9mmol/L (125mg/dL)
- 2 hr plasma glucose: < 7.8 mmol/L (140mg/dL)

IGT (World Health Organization 2006):

- Fasting plasma glucose: < 7mmol/L (126mg/dL)
- 2 hour plasma glucose: 7.8mmol/L (140mg/dL) ≤ IGT < 11mmol/L (200mg/dL)

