3.5 STUDY OUTCOME MEASURES

Primary outcome: Difference in 0 minutes glucose on 75g oral glucose tolerance test between the control arm and intervention arm at 6 weeks

Secondary outcomes: 120 minutes glucose on 75g oral glucose tolerance test
0 minutes glucose on 75g oral glucose tolerance test
HbA1c
Weight
BMI
Lean mass
Fat mass
Waist circumference
Total cholesterol
Fasting Triglycerides
LDL cholesterol
HDL cholesterol
HOMA Insulin sensitivity and secretion measurement
120 minute c-peptide following 75g oral glucose tolerance test
Systolic blood pressure
Diastolic blood pressure
Food frequency (by food frequency questionnaire and interviews) Energy intake
Carbohydrate intake
Fat intake
Saturated fat intake
Salt intake
Vitamin D
Vitamin B6
Vitamin B12

All secondary outcomes will be measured at 6, 12 and 26 weeks (with the exception of HbA1c which will only be measured at 12 and 26 weeks).

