6.2 STUDY SCHEDULE

6.2.1 SCREENING

Visit 1: Study preparation

- Send participants a Participant Invitation Letter (Appendix 8), and PIS (Appendix 6).
- Schedule a screening visit for potential participants.

Visit 2: Screening (Day -42 to -0 +/-10 working days)

- Discuss the consent procedure (Appendix 5) and any questions that a potential participant may have regarding the trial.

- If the potential participant would like to participate in the trial, they will be provided with an opportunity to sign the consent form and the PIS. A copy of the consent form will be provided to the participant and a copy will be retained by the clinical trial team.
- Review medical history to determine eligibility based on inclusion/exclusion criteria.
- Perform medical examinations needed to determine eligibility based on inclusion/exclusion criteria. This will include a finger prick blood sample that will be analysed either using a point-of-care HbA1c test using a Siemens DCA Vantage POCT device, or a lab analyser, to measure HbA1c levels.
- Send the GP letter (Appendix 7) to the GP of each confirmed participant in the trial who has consented to informing their GP of their participation in the trial.
- Provide participants with access to online and/or hard-copy food frequency questionnaire that they will need to complete for 1 week of food intake prior to their first clinical appointment in the trial (Visit 3).

Following confirmed enrolment in Visit 2, participants will undergo assignment to one of the three arms of the study.

Visit 3: Baseline clinical measurements (Day -21 +/- 10 working days)

- Verify inclusion/exclusion criteria and consent.
- Perform clinical assessment of glucose regulation and anthropometric measurements.
- Obtain urine pregnancy test (if applicable).
- Collect blood sample (15mL).
- Assess blood pressure, weight, height, waist circumference, lean body mass, and fat body mass.
- Perform 0 minutes on 75g glucose OGTT, 120 minutes on 75g glucose OGTT, 120 minutes c-peptide following 75g glucose OGTT, HOMA insulin sensitivity and secretion measurement.
- Provide two saliva samples (2mL each) via spit.
- Complete trial commencement questionnaire.

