## Study population

The study participants will be adults with impaired glucose regulation and fulfilling the following inclusion / exclusion criteria:

- Inclusion criteria
  - Provision of signed and dated informed consent form
  - Adults over 18 years of age
  - Impaired glucose regulation including IFG and IGT by FPG, OGTT or HbA1c criteria
  - Access to smartphone with an operating system of iOS 8.0 or above, or Android 4.0 or above.
- Exclusion criteria
  - Diabetic
  - Pregnant or planning pregnancy
  - Breastfeeding
  - Enrolled in other clinical trials
  - Have active malignancy or under investigation for malignancy
  - Severe visual impairment
  - Reduced manual dexterity
  - Use of psychiatric, anti-diabetic, and/or weight loss medication, and/or oral steroids
  - Bariatric surgery
  - History of illnesses that could interfere with the interpretation of the study results (e.g. HIV, Cushing syndrome, chronic kidney disease, chronic liver disease, hyperthyroidism, hereditary fructose intolerance, alcohol or substance abuse)
  - Unable to participate due to other factors, as assessed by the Chief Investigator

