#### - Per protocol population

In addition, the primary endpoint will be analysed with the Per Protocol population (PPP), which consists of those subjects in the ITT population who complete the study with no significant deviations from the planned protocol procedures. The exclusion will be as follows:

- Participants without impaired glucose regulation before inclusion [see definition page 6]
- Significant protocol deviation such as non respect of inclusion / exclusion criteria
- Pregnancy during follow-up
- Participants loss to follow-up or who withdrew consent

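### The SAP's glucose-based definition of impaired glucose tolerance reverses the fasting limit in Protocol 3.3, and the per-protocol exclusion relies on it

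*SAP*

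**What the plan says.** SAP, Definitions, describes the condition as "Impaired glucose regulation: impaired fasting glucose (IFG) or impaired glucose tolerance (IGT"). IFG needs FPG from 6.1 to 6.9 mmol/L with 2-hour glucose below 7.8. IGT has two bullets. The first, printed as a formula, joins FPG ≥ 7 mmol/L by AND to 2-hour glucose from 7.8 to below 11. The second is "HbA1c between 42 and 47 mmol/mol". No AND or OR links the two bullets.

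Protocol 3.3 has the same IFG limits and the same 2-hour range for IGT, but its fasting line for IGT reads "Fasting plasma glucose: < 7mmol/L (126mg/dL").

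SAP 1.6 analyses the primary endpoint in a per-protocol population as well as by intention to treat. The first exclusion from that population is "Participants without impaired glucose regulation before inclusion [see definition page 6"].

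On eligibility, the SAP's Study population section admits "Impaired glucose regulation including IFG and IGT by FPG, OGTT or HbA1c criteria", and Protocol 4.2 allows the same three routes.

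**The concern.** The two documents place glucose-based IGT on opposite sides of the same fasting limit. The SAP version is in use, because it decides who leaves the per-protocol population. Protocol 9.4 counts the per-protocol analysis among the tests of robustness of the primary result, so membership should follow one rule fixed in advance. The trial is also open label, which makes it undesirable to settle that rule late.

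As printed, the rule can misplace people in two directions. It can drop participants whom the protocol regards as having IGT. It can also count as impaired someone whose FPG lies above both fasting ranges in Protocol 3.3. The exclusion's pointer does not help the analyst: it cites page 6, where the SAP contents list puts the Background, while Definitions is listed on page 8.

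**Working it through.** The plan gives no figure to reproduce. The check sets the rules side by side.

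**Inputs** (F = FPG, G = 2-hour glucose, both in mmol/L)

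- Protocol 3.3, IGT: F < 7 and 7.8 ≤ G < 11
- SAP Definitions, IGT, first bullet: F ≥ 7 and 7.8 ≤ G < 11
- Both documents, IFG: 6.1 ≤ F ≤ 6.9 and G < 7.8
- SAP Definitions, IGT, second bullet: HbA1c 42 to 47 mmol/mol

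**Step 1: overlap of the two IGT rules.** One needs F < 7 and the other F ≥ 7, so they share no case. On a 0.1 mmol/L grid (F from 4.0 to 9.0, G from 4.0 to 13.0), the protocol rule covers 30 × 32 = 960 pairs, the SAP rule 21 × 32 = 672, and the overlap is 0. The 960 and 672 depend on the grid range and count no participants. Only the 0 carries information.

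**Step 2: does the SAP's IFG line recover the lost cases?** No. Protocol IGT needs G ≥ 7.8 and IFG needs G < 7.8. A participant with F < 7 and G from 7.8 to below 11 is therefore neither IFG nor glucose-based IGT in the SAP.

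**Step 3: example profiles**, with HbA1c below 42 unless shown, and the HbA1c bullet read as an alternative.

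| FPG | 2-hour glucose | HbA1c | Impaired by Protocol 3.3 | Impaired by SAP Definitions |
|---|---|---|---|---|
| 5.5 | 9.0 | below 42 | yes (IGT) | no |
| 6.5 | 9.0 | below 42 | yes (IGT) | no |
| 6.5 | 7.0 | below 42 | yes (IFG) | yes (IFG) |
| 7.2 | 9.0 | below 42 | no | yes (IGT) |
| 7.2 | 7.0 | below 42 | no | no |
| any | any | 42 to 47 | yes | yes |

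**Step 4: who can be misplaced?**

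- HbA1c 42 to 47: nobody is reclassified if the HbA1c bullet is an alternative. The eligibility wording in the SAP's Study population section supports that reading. If the bullets were a joint condition, a person qualifying on HbA1c alone would not count as IGT, so the missing link word matters.
- HbA1c 48 or above: Protocol 4.1 classes this as type 2 diabetes, which is an exclusion. SAP 1.6 separately removes eligibility breaches, so these people leave the per-protocol population whichever way the sign reads.
- HbA1c below 42: here the sign decides. A participant admitted on OGTT-defined IGT is dropped under the SAP wording. A participant with F ≥ 7 and G from 7.8 to below 11 counts as impaired.

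**Step 5: how many?** The documents do not say how many participants enter on glucose criteria with HbA1c below 42. The lower limit is 0. Each such person is 1 of 60 in an arm (1/60 = 1.7%).

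**The case against.** The strongest objection is that the definition has almost no route to a result. At the screening visit, "This will include a finger prick blood sample that will be analysed either using a point-of-care HbA1c test" or a laboratory analyser, and no OGTT is scheduled there. Protocol 6.2.1 continues, "Following confirmed enrolment in Visit 2, participants will undergo assignment to one of the three arms of the study", and the first trial OGTT comes later, at Visit 3. The only glycaemic test that the trial schedules before assignment is therefore HbA1c, so the HbA1c bullet is the one that would normally operate. This largely stands and is why the point is minor. It does not remove the point, because both documents admit people on fasting glucose or OGTT, and Protocol 4.4 recruits some people already identified as prediabetic in standard care.

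A second objection is that the contradiction rests on one symbol in a formula extracted from PDF. The sign is explicit in the text supplied, but it should be checked in the source file before anything is changed.

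A reader might also infer that the logistic regression of the proportion with impaired glucose regulation would be misclassified, most clearly at week 6, since the protocol measures all secondary outcomes at each review "with the exception of HbA1c which will only be measured at 12 and 26 weeks". The documents do not support stating this as an error. That regression appears only in Protocol 9.4, the SAP does not carry it, and the protocol has its own definition. The misclassification would arise only if the regression were run using the SAP definition.

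**Conclusion.** The contradiction is real as printed, and the rule that depends on it should not be applied until the two sections agree. The severity is minor, because only a supplementary per-protocol analysis is affected.

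A reader might infer that the primary result is at risk, or that anyone with HbA1c outside 42 to 47 would be misplaced. Neither follows. The primary intention-to-treat analysis models week 6 FPG as a continuous outcome in everyone randomised and does not use the definition. Above the HbA1c range, the diabetes exclusion applies in any case. The exposure is limited to participants who qualified on glucose criteria, or are judged by them, with HbA1c below 42.

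The conclusion that few are affected rests on two assumptions: most participants enter through the HbA1c screening test, and the HbA1c bullet is an alternative criterion. I take no view on which side of 7 mmol/L is clinically right, only that the two sections must be reconciled.

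**What to change.** 1. Check the inequality sign in the SAP source file.
2. Reconcile the IGT definition in the SAP's Definitions section with Protocol 3.3.
3. State in that section that the HbA1c bullet is an alternative (OR) criterion, consistent with the SAP's own eligibility wording.
4. Correct the page pointer in the first per-protocol exclusion of SAP 1.6, or cite the section by name.
5. Use the one reconciled definition for the per-protocol exclusion, and for the Protocol 9.4 comparison of proportions with impaired glucose regulation if it is run.

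The cost is a few lines of SAP text. Data collection, sample size and the primary analysis do not change.
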